6.2. Treatment Assignment

Subjects will be assigned to Treatment Group 1 or Treatment Group 2 in accordance with a balanced independent randomization schedule generated prior to the start of the study. A corresponding set of randomization envelopes (one per subject) will be generated. A

randomization envelope for each subject will be opened prior to dosing (on day -1) to reveal the subject's treatment assignment. This process will ensure that study personnel and the volunteers will have no knowledge of the next treatment to be assigned.

Once a randomization number has been assigned to a subject, it will not be re-assigned to another subject. Randomization numbers will be assigned sequentially as subjects become eligible for dosing.

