The t-statistics for the boundaries, as calculated in East 5.4, are 1.0274 for interim 1, 0.4437 for interim 2 and -1.645 for the final analysis. These correspond to p-values for the t-test of $p=.848$ at interim 1, $p=.671$ at interim 2, and $p=.05$ for the final analysis.

The clinical interpretation of these thresholds is easier to evaluate if they are converted to thresholds for the GMC ratio. The challenge with this conversion is that the thresholds for the GMC ratios that will lead to a futility result or a result of non-inferiority will be dependent on the variability in the estimates observed in the trial. However, a conversion can be made assuming the standard deviation will match the one used in the sample size calculation of 0.75. Under this assumption, the log transformed scale the boundaries correspond approximately to an observed difference in the means of $>.4575$ at interim 1 and $>.242$ at interim 2, or observed GMC ratios of > 2.87 and >1.75 respectively. The threshold for success at the final analysis would be an observed GMC ratio of 1.173 or less.

Given the high level of variance of anti-PA antibody levels at week 4 with AVA (as observed in [Marano, 2008](#)), it is challenging to estimate either the GMC or the GMC ratios with precision without a very large sample size. The total sample size was determined based on how many subjects were required to have an 80% chance of ruling out that the GMC ratio was >1.5 when it was truly 1. Many more subjects would be required to estimate the actual ratio with considerable precision.

Similarly the interim analyses will not result in precise estimates of the GMC ratio. There will be sufficient data collected to determine whether it is futile to expect that the trial would result in a non-inferiority conclusion. The beta error spending boundary was chosen such that approximately 25% of the Type II error is spent in the first interim. There was a willingness to allow for this much error in the first interim after only 30 subjects, because it is assumed that there is a high likelihood the anti-PA antibody levels will be inferior when raxibacumab is given with AVA, based on the results of the [Malkevich \(2013\)](#) paper.

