2.4 Sample Size

The sample size calculation is based on the assumption that the individual values will be analyzed after being transformed by \log_{10} resulting in data that is approximately normal. In the transformed data the analysis of the ratio of means is equivalent to a difference of mean values with a margin of $\log_{10}(1.5) = 0.176$. The standard deviation of the \log_{10} transformed data is assumed to be 0.75.

The sample size is calculated assuming 1:1 randomization and two interim analyses for futility after 30 and 100 analyzable subjects. The boundaries for the futility analysis are based on Rho family error spending function with a rho of 0.5. For the purposes of the sample size calculation, the power will be calculated under the alternative hypothesis setting, where the ratio is 1, or equivalence between the two arms with respect to concentrations of anti-AP antibody. With a one-sided type I error of 5% a sample size of 534 subjects will allow for 80% power to make a claim of non-inferiority (margin of 1.5), if the true ratio between the geometric means is 1.

In a trial of 534 patients, the largest observed GMC ratio between the AVA and the combination that results in a statistically significant non-inferiority result is an estimated ratio of 1.173. This can alternatively be viewed as a minimum observed anti-PA concentration due to the addition of AVA in the combination of ~85% of the concentration when AVA is administered alone. This is under the assumption that the observed variability in the study population is similar to the study design assumption.

Details on the sensitivity analyses of sample size determination can be found in Section 9.2.2 of the study protocol.

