4.6 Demographic and Baseline Characteristics

Individual subject demographics and baseline characteristics (medical history and results from urine drug and alcohol screens, serology screening, and pregnancy tests) will be presented in listings.

Demographic characteristics such as age, sex, race, ethnicity, height, weight, and body mass index (BMI) will be summarized and tabulated by treatment and for all subjects overall. Descriptive statistics will be presented for age, height, weight, and BMI. Frequency counts and percents will be presented for sex, race, and ethnicity.

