4.11 Primary Analysis

At the final analysis, the non-inferiority test will be based on the CI for the ratio of anti-PA Ab (attributable to AVA) GMCs between the AVA and the AVA + raxibacumab groups at Week 4. This analysis will be performed in the per-protocol population. If the upper bound of the 90% CI is less than 1.5, non-inferiority will be established.

This analysis will be repeated in a sensitivity analysis which will use the full ITT population with imputation for subjects without Week 4 anti-PA Ab concentration results. Two methods of imputation will be used for subjects without Week 4 anti-PA Ab concentration results:

1. In the AVA + raxibacumab arm, missing data will be imputed with the first quartile from the non-missing data in this arm. In the AVA arm, missing data will be imputed with the third quartile from the non-missing data in this arm.
2. In the AVA + raxibacumab arm, missing data will be imputed with the lower limit of quantitation (LLQ). In the AVA arm, missing data will be imputed with the maximum from the non-missing data.

The GMCs for each treatment group will be summarized with corresponding 95% CI for the Week 4 timepoint as well as Week 8 and Week 26.

The GMC ratio and GMCs within each cohort and corresponding CIs will be calculated by first log transforming all of the data by a log base 10. A t-test will be performed and CIs will be calculated about the mean logs and the difference of the mean logs. The results will be transformed back to the original scale by exponentiation, again using a base 10. The exponentiated differences of the sample mean logs will be the ratio of the sample geometric means of the untransformed results.

Welch's unequal variances *t*-test will be performed to assess the sensitivity of the results to the assumption of equality of variances between the anti-PA Ab concentrations in the two treatment groups.

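### The primary t-test on log10 Week 4 anti-PA is valid and correctly powered, but leaves collected age, sex and BMI unused where the protocol calls precision challenging

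*SAP*

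**What the plan says.** **Primary test.** SAP 4.11 log-transforms the Week 4 values and compares the two arms: "A t-test will be performed and CIs will be calculated about the mean logs and the difference of the mean logs". The decision rule is "If the upper bound of the 90% CI is less than 1.5, non-inferiority will be established". Protocol 9.4.1 plans the same test. The sensitivity analyses in SAP 4.11 (ITT with two imputation rules, and a Welch test) also contain no covariate.

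**Design.** SAP 2.4: "With a one-sided type I error of 5% a sample size of 534 subjects will allow for 80% power", which applies "if the true ratio between the geometric means is 1". The SD of the log10 "transformed data is assumed to be 0.75". Protocol 9.2.1 adds that the results of the cited earlier vaccine trial pointed closer to 0.85.

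**Covariates.** SAP 4.6: "Demographic characteristics such as age, sex, race, ethnicity, height, weight, and body mass index (BMI) will be summarized". SAP 4.1 takes the pre-dose Day 1 value as baseline for anti-PA. Men and women aged 18 to 65 are eligible (Protocol 5.1), and the vaccine dose is a fixed 0.5 mL. Treatment is assigned from a "balanced independent randomization schedule generated prior to the start of the study" (Protocol 6.2), and no stratification factor is named.

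**Variance.** Protocol 9.3.2 begins its remark on precision with "Given the high level of variance of anti-PA antibody levels at week 4 with AVA" and concludes that precise estimates would need a very large sample. Protocol 9.2.3 plans no sample size re-estimation.

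**The concern.** A covariate that predicts Week 4 anti-PA and is left out of the model leaves its share of the variance in the standard error. It also leaves any chance imbalance on that covariate in the estimated ratio. The trial has few other ways to gain precision. N is fixed, the assumed SD is below the value that the protocol itself draws from the earlier trial, and the protocol's tables show 67.6% power at SD 0.9 (Table 6) and 59.0% at a true ratio of 1.11 with SD 0.75 (Table 5). Adjustment for variables already collected needs no further subjects. At stake are a few points of power and a somewhat narrower interval. The validity of the test is not in question.

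**Working it through.** **Inputs from the documents.** Margin log10(1.5) = 0.1761; SD 0.75; N = 534, 1:1; one-sided 5% (final critical value −1.645); futility looks at 30 and 100 analyzable subjects; beta spending with rho = 0.5; futility boundaries 1.0274 and 0.4437 (SAP 4.9).

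**Step 1: reproduce the plan's figures.**
- Standard error at N subjects: SD × √(4/N). At 534: 0.75 × √(4/534) = 0.0649.
- Power with no interims: Φ(0.1761/0.0649 − 1.645) = Φ(1.07) = 85.7%.
- Beta spent: 0.2 × √(30/534) = 0.0474, then 0.2 × √(100/534) = 0.0865 in total. Solving for the boundaries gives 1.0276 and 0.4438 (stated: 1.0274 and 0.4437).
- Power with both looks, from the trivariate normal distribution with correlations √(n_i/n_j): 79.99% (stated: 80%).
- Largest passing ratio: 10^(0.1761 − 1.645 × 0.0649) = 1.173 (stated: 1.173).
- At SD 0.9 the same method gives 67.4% (Table 6, simulated: 67.6%).

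The unadjusted design is therefore sound as written.

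**Step 2: adjust the final look only.** R² is the share of variance explained. It is an assumption, since neither document gives one.
- Final standard error: SD × √(1 − R²) × √(4/534). At SD 0.75 and R² 10%: 0.7115 × √(4/534) = 0.0616.
- The interim statistics keep the full SD and the stated boundaries. Their correlation with the adjusted final statistic is √(1 − R²) × √(n/534).

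| Assumed R² | Power, SD 0.75 | Power, SD 0.85 | Largest passing ratio, SD 0.75 |
|---|---|---|---|
| 0 | 80.0% | 71.5% | 1.173 |
| 5% | 81.2% | 73.0% | 1.180 |
| 10% | 82.5% | 74.5% | 1.188 |
| 20% | 84.9% | 77.6% | 1.204 |

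**Step 3: cost if the covariates explain nothing.** With k useless covariates the expected variance inflation is about 1 + k/(534 − 3 − k). For k = 4 this is 1 + 4/527 = 1.0076, and power at SD 0.75 goes from 80.0% to 79.8%. Three covariates give 1 + 3/528 = 1.0057, also 79.8%.

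**Step 4: what Day 1 anti-PA could add.** Protocol 5.2 excludes prior PA vaccination and screening values above 2 × LLOQ. Suppose that Day 1 values keep to that limit and that values below LLOQ are set to LLOQ. Their log10 span is then log10(2) = 0.301. The SD is 0.301/√12 = 0.087 if they are uniform, and at most 0.301/2 = 0.151.
- R² = (slope × SD of baseline)² / 0.75². With an assumed slope of 1 this is 1.3% to 4.0%, which lies below the 5% row of the table.
- A slope of 2 would give about 5% to 16%, but only if values really spread over the whole permitted range. In PA-naive subjects most should sit at or near LLOQ.

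**The case against.** **The t-test is not wrong.** This stands. It is valid under randomization, the SD of 0.75 is for unadjusted data, and the sample size was built on the unadjusted test. A reader might infer that the trial is underpowered or biased because it ignores covariates or does not stratify. The documents do not support that: every design figure reproduces.

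**No gain can be shown from the documents.** This stands for the size of the gain. Neither document relates age, sex or BMI to Week 4 anti-PA, and at R² of 5% the gain is only about 1.2 points. It does not defeat the point, because the decision does not need R²: adjustment breaks even at an R² of about 0.8%, and the loss below that is about 0.2 points at most.

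**Day 1 anti-PA is a weak covariate.** This also stands. Listing it as an equal source of lost precision would ignore the entry criteria.

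**Some figures would overstate the gain.** Applying the reduced SD at all three looks gives 83.2% at R² 10% and 86.4% at 20% (SD 0.75). Those figures do not apply when the interim tests stay unadjusted, which is why the table adjusts only the final look.

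**The interims should use the primary model.** This is a reasonable preference. Unadjusted interims keep the published boundaries usable, however, and do not inflate type I error: the final critical value is unchanged, and stopping for futility can only reduce rejections.

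**The protocol is easily over-read.** It calls precise estimation challenging and does not name variance as its chief difficulty. The fairly rapid drop in Protocol 9.2.2 refers to growing interference with the vaccine response. For the higher SD of 0.9 it reports a fall in power to 65–70%.

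**Conclusion.** The point holds as one of efficiency. SAP 4.11 specifies a valid and correctly powered test that leaves age, sex and BMI unused. Prespecified adjustment would raise power by about 1.2, 2.5 and 4.9 points at R² of 5%, 10% and 20% with SD 0.75, and by about 1.5, 3.0 and 6.1 points with SD 0.85. All of these R² values are assumed. The figures also assume a true ratio of 1, 534 analyzable subjects, the stated boundaries, equal SD in both arms and adjustment at the final look only. Even an R² of 20% at SD 0.85 does not restore 80% power, so adjustment is no substitute for a correct SD. The case rests on the asymmetry: a possible gain of several points against a worst case of about 0.2.

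**What to change.** Before the first interim, amend SAP 4.11 as follows:

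- **Primary estimate:** a linear model on log10 Week 4 anti-PA with treatment, age, sex and BMI in the per-protocol population. Back-transform the adjusted difference and its 90% CI to the GMC ratio, with the same 1.5 margin.
- **Day 1 anti-PA:** log10 Day 1 anti-PA may be added as an optional covariate. If it is, state that values below LLOQ are set to LLOQ, the rule that SAP 4.12.1 already gives under the Week 8 and 26 analyses.
- **Sensitivity analyses:** keep the unadjusted t-test and the Welch test, and apply the adjusted model to both ITT imputation analyses.
- **Interims:** state that the futility tests in SAP 4.9 remain unadjusted, so that the stated boundaries still apply.
- **Record:** list the change in SAP 4.13, since Protocol 9.4.1 describes the unadjusted test.

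The cost is a few sentences of SAP text and one standard model. The covariates are already collected, and no subjects or visits are added.

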4.12 Secondary Analysis

4.12.1 Anti-PA Antibodies

Anti-PA antibody concentrations will also be collected at Weeks 8 and Week 26 after the first AVA dose. Values less than BLQ will be set to lower limit of quantitation (LLOQ). The GMCs with corresponding 95% CI will be summarized for each treatment group at each timepoint. No comparison between treatments will be made. There will be no imputation for subjects with missing data at a given timepoint.

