As a secondary endpoint, ratios of the anti-PA Ab GMC for each treatment group at Weeks 8 and 26 will be calculated as described above.

TNA geometric mean titers (GMTs) along with 95% CI will be summarized for each treatment group at each timepoint. The percentage of subjects, along with 95% CI, who seroconvert, defined as a >4-fold increase in TNA titer will be summarized, at Weeks 4, 8 and 26 after the first AVA dose for both arms separately.

Clinical safety observations will include AEs, urinalysis, vital sign measurements, and clinical laboratory assessments. Safety data will be tabulated and, where appropriate, analyzed by the use of descriptive statistics. Safety data will be tabulated for the safety population.

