9.4.2. Secondary Analyses

9.4.2.1. Anti-PA Antibodies

Anti-PA antibody concentrations will also be collected at weeks 8 and 26 after the first AVA dose. The GMCs along with 95% CI will be summarized for each treatment group at each timepoint. There will be no imputation for subjects with missing data at a given timepoint.

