2.1.2 Secondary Objective(s)

- To compare the immunogenicity of AVA at Week 8 and 26 after the first AVA dose, when AVA is administered alone or concomitantly with raxibacumab.
- To estimate and compare seroconversion, defined as a ≥ 4 -fold increase in toxin neutralizing activity (TNA) titer from baseline, at Weeks 4, 8 and 26 after the first AVA dose, when AVA is administered alone or concomitantly with raxibacumab.

- To describe the safety of AVA when co-administered with raxibacumab versus AVA alone.

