2.2.2 Secondary Endpoint(s)

- Ratio of GMC of anti-PA Ab at Weeks 8 and 26 after the first AVA dose, between the AVA alone and the AVA with raxibacumab treatment groups.
- Percentage of subjects who seroconvert, at Weeks 4, 8, and 26 after the first AVA dose, between the AVA alone and the AVA with raxibacumab treatment groups.
- Rates of reported adverse events (AE) as well as review of vital signs, urinalysis, and clinical laboratory data in the AVA alone and the AVA with raxibacumab treatment groups.

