4.13 Changes from Analyses Planned in Protocol

Electrocardiogram intervals will be listed for only those subjects that had the procedure performed after experiencing an AE.

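### The SAP rules out any treatment comparison of anti-PA at Weeks 8 and 26, so the between-arm GMC ratio named as a secondary endpoint is never estimated

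*SAP*

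**What the plan says.** SAP 2.1.2 gives a secondary objective: "To compare the immunogenicity of AVA at Week 8 and 26 after the first AVA dose", with AVA given alone or with raxibacumab. SAP 2.2.2 gives the matching endpoint: "Ratio of GMC of anti-PA Ab at Weeks 8 and 26 after the first AVA dose", taken between the two treatment groups. The protocol has the same objective and endpoint in its synopsis and in Section 3. The Analysis part of the synopsis adds that "ratios of the anti-PA Ab GMC for each treatment group at Weeks 8 and 26 will be calculated as described above", which refers back to the log10 t-based method for the Week 4 ratio.

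SAP 4.12.1 covers anti-PA at Weeks 8 and 26. It plans per-arm GMCs with 95% CIs and then says "No comparison between treatments will be made". SAP 4.11 likewise mentions Weeks 8 and 26 only for per-arm GMCs. SAP 4.13, on departures from the protocol, has a single entry: "Electrocardiogram intervals will be listed for only those subjects that had the procedure performed after experiencing an AE".

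**The concern.** A ratio of one arm's GMC to the other's is a comparison between treatments. A statistician who programs from SAP 4.12.1 would not produce the secondary endpoint defined in SAP 2.2.2, and nothing in SAP 4.13 shows that the omission was intended.

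The later visits matter to the purpose of the trial. Protocol 4.4 says AVA is expected to carry protection beyond the roughly 28 days covered by raxibacumab. It chose 26 weeks so that the durable response could be assessed once raxibacumab is essentially gone. At Week 4 the vaccine-attributable concentration is obtained by subtracting serum raxibacumab from the assay result (SAP 3.2). By Week 26 there should be little left to subtract. The plan collects these samples but gives no effect estimate or interval for them. Readers would have to judge two separate intervals by eye, which is a poor way to detect a difference.

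**Working it through.** **The texts side by side**

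| Place | Between-arm ratio at Weeks 8 and 26 |
|---|---|
| Protocol synopsis and Section 3, objectives and endpoints | Named as the endpoint |
| Protocol synopsis, Analysis | To be calculated |
| Protocol 9.4.2.1 | Not mentioned; per-arm GMCs only |
| SAP 2.1.2 and 2.2.2 | Comparison is the objective; ratio is the endpoint |
| SAP 4.11 | Per-arm GMCs for these weeks; the ratio method names no timepoint |
| SAP 4.12.1 | Comparison excluded |
| SAP 4.13 | No change declared |

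The contradiction is textual and needs no arithmetic. The arithmetic below shows what is lost.

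**Inputs.** The log10 SD is 0.75 and there are 267 analyzable subjects per arm (Protocol 9.2.1 and 4.3; SAP 2.4 and 2.3). Both are Week 4 planning values. Using them at Weeks 8 and 26 is an assumption, because the documents give no figures for those visits.

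**The plan's own precision figure, reproduced.** Protocol 9.3.2 gives a final standard error of 0.065 and a 90% CI that scales the ratio by 1.28.
- SE = 0.75 × √(2/267) = 0.0649.
- 90% half-width = 1.648 × 0.0649 = 0.107, and 10^0.107 = 1.28. This agrees.

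**95% CI for the ratio.** 1.964 × 0.0649 = 0.1275, and 10^0.1275 = 1.34. The interval excludes 1 once the observed ratio exceeds about 1.34.

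**What SAP 4.12.1 would report instead.**
- Per-arm 95% half-width = 1.969 × 0.75/√267 = 0.0904, and 10^0.0904 = 1.23.
- With equal SDs, the two intervals separate only when the log10 difference exceeds 2 × 0.0904 = 0.181, an observed ratio of about 1.52.
- In standard errors that is 0.181/0.0649 ≈ 2.78, a two-sided p of about 0.005.

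Observed ratios between 1.34 and 1.52 would therefore exclude 1 at the 5% level while the two displayed intervals still overlapped.

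**Range over assumed inputs.** SD 0.90 is the protocol's own sensitivity value (9.2.2). The 214 per arm assumes 20% missing at the later visit. The last column is the square of the per-arm factor.

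| SD | n per arm | 90% CI factor | 95% CI factor | Per-arm 95% factor | Ratio at which per-arm CIs separate |
|---|---|---|---|---|---|
| 0.75 | 267 | 1.28 | 1.34 | 1.23 | 1.52 |
| 0.75 | 214 | 1.32 | 1.39 | 1.26 | 1.59 |
| 0.90 | 267 | 1.34 | 1.42 | 1.28 | 1.65 |
| 0.90 | 214 | 1.39 | 1.48 | 1.32 | 1.75 |

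The gap between the last column and the 95% CI factor remains in every row.

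**The case against.** The strongest point is that the protocol is itself divided. Protocol 9.4.2.1, the body section on this analysis, says only "The GMCs along with 95% CI will be summarized for each treatment group at each timepoint" and does not mention a ratio, so SAP 4.12.1 follows that section closely. This stands as a description. However, 9.4.2.1 is silent where the SAP prohibits, and the protocol's objective, endpoint and synopsis analysis text all call for the ratio.

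Second, the ratio paragraph in SAP 4.11 names no timepoint and directly follows the sentence on Weeks 8 and 26, so it might be read as covering them. It sits under the primary analysis, though, and the specific exclusion in 4.12.1 governs those weeks. If both were meant to apply, the SAP contradicts itself. The exclusion might also be meant to rule out only a hypothesis test, but the SAP does not say so and lists no ratio among the outputs.

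Third, a reader can divide the two GMCs and rebuild the interval, because the arms are independent: √(0.0904² + 0.0904²) = 0.128, or ×/÷ 1.34. That is correct arithmetic, but it is not a planned analysis, and its method and confidence level would be chosen after the results were known.

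Fourth, the figures depend on full enrolment. After a futility stop at 30 or 100 subjects (15 or 50 per arm, SE 0.274 or 0.15 in Protocol 9.3.2), the 95% factor would be about 3.6 or 2.0. This limits the precision of the ratio but does not justify omitting it.

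Finally, no alpha, margin or power claim attaches to this endpoint, and the Week 4 test, sample size and futility rules are unaffected. That limits the consequences but leaves the contradiction in place.

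**Conclusion.** The point holds. SAP 4.12.1 as written excludes the analysis that defines a stated secondary endpoint, and SAP 4.13 does not declare the change. The finding rests on current text in both documents and does not depend on any numerical assumption.

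The size of the loss does depend on assumptions. If the Week 4 SD and number per arm carry over, the plan forgoes a 95% interval of about ×/÷ 1.34 for the ratio. The per-arm display it offers would conceal differences that produce observed ratios of about 1.34 to 1.52. With SD up to 0.90 and 20% missing, the forgone 95% interval widens to about ×/÷ 1.48, which is still informative about the durable response. The Week 4 primary analysis is not touched.

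**What to change.** In SAP 4.12.1, delete the sentence that excludes a comparison. In its place, state that the AVA/(AVA + raxibacumab) GMC ratio at Week 8 and at Week 26 will be estimated with its CI by the log10 t-based method of SAP 4.11, as a secondary analysis without a formal non-inferiority claim. Name two details:

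- **Population.** SAP 4.1 already assigns immunogenicity summaries to the Per Protocol population, so this would be Per Protocol subjects with a value at that visit.
- **Confidence level.** 95% would match the per-arm intervals in the same section; 90% would match the primary analysis.

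Add the same statement to Protocol 9.4.2.1 at the next amendment so that it agrees with the synopsis. If the sponsor really intends no comparison, the alternative is to amend the objective and endpoint in both documents and declare the change in SAP 4.13.

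The same edit should check SAP 4.12.2: the objective is to estimate and compare TNA seroconversion, but the analysis summarizes each arm separately.

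The cost is a short SAP edit and one extra row per timepoint in an existing table. No new data, subjects or alpha are needed. It should be made before anyone on the study team sees comparative results, so that the ratio counts as prespecified.
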